7.4 Outcomes

See Section 8.2 for analysis of outcomes.

8. DATA COLLECTION AND QUALITY ASSURANCE

8.1 Data Collection Forms

Appended to the protocol are case report forms (CRF) that will be used for all other clinical

data. The patients name or other identifying information is never recorded on the CRF or recorded by those individuals involved in the outcome assessments. Rather a unique study code # is given to each patient without regard to randomization treatment group. Laboratory reports and informed consent forms that do identify the study patients are maintained with a key of unique study code # in a locked cabinet in the clinical research unit with a back up list in the PI's office.

8.2 Data Management

This is a single site study. Our data management procedures are mature and standardized. Data are entered from the CRFs and outcome assessment forms into ACCESS, which allows ranges to be defined a priori, minimizing data entry errors. Data will later be imported into SPSS, and within- and cross-file checks are used for cleaning and checking anomalous values. Data files are backed-up regularly to a secure server.

8.3 Quality Assurance

8.3.1 Training

We use centralized training, certification, and reliability testing for consistency across projects. In addition, monthly staff meetings will be held to review and remind staff on data collection, informed consent, adverse events, confidentiality, etc, to research staff to enhance fidelity.

8.3.2 Quality Control Committee

Not applicable.

8.3.3 Metrics

We have developed reproducibility methods for all outcome assessments. These methods allow us to develop a range of coefficients of variation for the various measures over time.

8.3.4 Protocol Deviations

The project manager of the study and project statistician will regularly be reviewing the individual case report forms for deviations from the protocol as data are entered into the ACCESS database. Protocol deviations will be minimized by effective communication among clinical staff and study participants. In all cases, the deviations will be documented in a separate study binder and those of important magnitude must be reported to the University of Connecticut Institutional Review Board for assessment.

8.3.5 Monitoring

As this is a single center study, external monitoring will not be in place. The institution does have a voluntary (and random involuntary) auditing process in place for all Human Subjects Trials that is conducted by an officer of the Office of Clinical and Translational Research. In these audits, a random sample of CRFs are evaluated for protocol violations, as well as assessment of regulatory documents, informed consent forms and pharmacy records.

9. PARTICIPANT RIGHTS AND CONFIDENTIALITY

9.1 Institutional Review Board (IRB) Review

The study protocol and the informed consent document has been reviewed and approved by the IRB committee responsible for oversight of the study (University of Connecticut Health Center IRB). Any subsequent modifications will be reviewed and approved by the University of Connecticut Health Center IRB.

9.2 Informed Consent Forms (Appendix)

A signed informed consent form (ICF) will be obtained from each participant. The ICF will describe the purpose of the study, the procedures to be followed, and the risks and benefits of participation. A copy will be given to each participant and this fact will be documented in the participant's record.

9.3 Participant Confidentiality

Any data, forms, reports, and other records that leave the site will be identified only by a participant identification number (Participant ID) to maintain confidentiality. All records will be kept in a locked file cabinet. All computer entry and networking programs will be done using participant IDs only. Information will not be released without written permission of the participant, except as necessary for monitoring by IRB, the FDA, the NIA, and the OHRP.

9.4 Study Discontinuation

The study may be discontinued at any time by the IRB, the NIA, the OHRP, the FDA, or other government agencies as part of their duties to ensure that research participants are protected.

10. COMMITTEES (NOT APPLICABLE OTHER THAN DSMB – SINGLE CENTER STUDY)

11. PUBLICATION OF RESEARCH FINDINGS

Publication of research findings are under the direction of the Principal Investigators and other Key Personnel.

13. APPENDIXES

**Addendum to Protocol
11 – 01 - 2012**

Sleep Assessment:

The relationship between brain white matter disease and sleep will be evaluated using two different instruments which have both been validated in older individuals.

The Epworth Sleepiness Scale (ESS) is a self-administered questionnaire which has been shown to provide a measurement of the subject's general level of daytime sleepiness^{1;2}. This 8-item instrument evaluates the extent of subject sleepiness during various normal daytime activities.

The Pittsburgh Sleep Quality Index (PSQI) offers a quantitative assessment of subjective sleep difficulties experienced by each individual^{3;4}. The instrument generates “component” scores: subjective sleep quality, sleep latency, sleep duration, habitual sleep efficiency, sleep disturbances, use of sleeping medication, and daytime dysfunction. The sum of scores for these seven components yields one global score^{3;4}.

The sleep assessments will be administered at baseline, 18- and 36- month timepoints.

Reference List

1. Johns MW. A new method for measuring daytime sleepiness: the Epworth sleepiness scale. *Sleep* 1991;14:540-545.
2. Johns MW. Reliability and factor analysis of the Epworth Sleepiness Scale. *Sleep* 1992;15:376-381.

Hearing Sub-study Bibliography

4. Musiek, F.E., & Baran, J.A. (2007). *The Auditory System: Its Anatomy, Physiology and Clinical Correlates*. Boston, MA: Allyn & Bacon.

**Intensive Versus Standard Blood Pressure Lowering to Prevent
Functional Decline in Older People**

NCT01650402

Statistical Analysis Plan

IRB Approval Version 9/25/2018

INFINITY Statistical Analysis Plan (modification)

IRB Review
IRB NUMBER: IE-11-155S-2
IRB APPROVAL DATE: 09/25/2018

Principal Investigators: [name], [name]
Senior Statistician: [name]
Project Statistician: [name], MS
Date: 24 September 2018

Amendment 1.1

The primary objective of the INFINITY Trial is to assess causality between 24-hour systolic BP levels and preservation of mobility, cognitive and urinary function associated with reduced accrual of small vessel disease of the subcortical white matter in people over the age of 75 years.

A key hypothesis of the trial is that intensive treatment of 24-hour systolic BP to levels of 130 mmHg or less will result in improved gait time, stair descent time, and maximal gait velocity compared to treatment of 24 hour systolic BP to levels of 145 mmHg or less. This separation of ambulatory BP goals should achieve at least a ≥ 10 mmHg differences between groups over time. Previously, this difference has been shown to be responsible for the mobility decrements associated with WMH in older patients with systolic hypertension in a prospective cohort study (Circulation. 2011;124 (21):2312-9. doi: 10.1161/CIRCULATIONAHA.111.037036).

Prior to database lock of this trial in October 2018, we have added several secondary analyses to be pre-specified with their rationale as needed.

1. Change in white matter hyperintensity (%) (WMH) from baseline to 3 years
 - a. According to treatment group (primary analysis)

$$\begin{aligned} Y_{i1} &= \beta_0 + \beta_C x_i + \gamma_i + \varepsilon_{i1} \\ Y_{i2} &= \beta_0 + \beta_C x_i + \beta_L + \beta_T x_i + \gamma_i + \varepsilon_{i2} \end{aligned} \tag{1.1}$$

Here, x_i is the treatment group indicator for participant i (one for intervention, zero for comparison); Y_{i1} is the WMH % for participant i at time 1 (baseline); Y_{i2} is the WMH % for participant i at time 2 (36 month follow-up); β_0 is interpreted as the average WMH % at baseline in the reference group; β_C is interpreted as the difference in the average WMH % at baseline between the intervention group and the reference group and will be zero if the two groups are exactly comparable in their baseline values; β_L is interpreted as the average change in WMH % between 36 month follow up and baseline in the reference group; β_T is interpreted as the difference average change in WMH % between 36 month follow up and baseline between the intervention group and the reference group and thus the parameter of primary interest; γ_i is a random intercept for participant i that addresses the correlation in WMH % across the two time points; and ε_{i1} and ε_{i2} are the residual error terms at baseline and follow-up, respectively. All analyses will be repeated as stratified analyses (b - e below).

- b. Stratified according to < or > median age
- c. Stratified according to gender
- d. Stratified according to median years of education
- e. Stratified according to a clinical diagnosis of minor or major depression
- f. Stratified according to presence or absence of statin therapy for hyperlipidemia
- g. Stratified according to presence or absence of anti-platelet therapies (aspirin, clopidigrel)
- h. Sensitivity analysis at 36 months by ambulatory systolic BP : rationale – for study patients who either never met the achieved BP for their group assignment or who shifted mid-trial to an ambulatory BP

value out of alignment with their assigned treatment group (e.g. a standard group patient whose 24 hour systolic BP was < 135 mmHg would be excluded from the sensitivity analysis; an intensive group patient whose 24 hour systolic BP was > 135 mmHg would be excluded from the sensitivity analysis).

2. Change in mobility, cognition and depression from baseline to 3 years
 - a. According to treatment group (primary analysis)

$$Y_{i1} = \beta_0 + \beta_C x_i + \gamma_i + \varepsilon_{i1}$$

$$Y_{i2} = \beta_0 + \beta_C x_i + \beta_L + \beta_T x_i + \gamma_i + \varepsilon_{i2}$$

Here, x_i is the treatment group indicator for participant i as in (1); Y_{i1} is the mobility score for participant i at time 1 (baseline); Y_{i2} is the mobility score for participant i at time 2 (36 month follow-up); β_0 is interpreted as the average mobility score at baseline in the reference group; β_C is interpreted as the difference in the average mobility score at baseline between the intervention group and the reference group and will be zero if the two groups are exactly comparable in their baseline values; β_L is interpreted as the average change in mobility between 36 month follow up and baseline in the reference group; β_T is interpreted as the difference average change in mobility between 36 month follow up and baseline between the intervention group and the reference group and thus the parameter of primary interest; γ_i is a random intercept for participant i that addresses the correlation in mobility across the two time points; and ε_{i1} and ε_{i2} are the residual error terms at baseline and follow-up, respectively.

This analysis will be repeated for each mobility parameter (gait speed, four stair ascent and descent time, supine to sit time), cognition scores (Trailmaking A and B, Stroop Color & Word score, and simple reaction time), and the Geriatric Depression Scale. The timed measures – Trailmaking A and B, and simple reaction time – will be inverse-transformed so that they have a speed interpretation; this will also reduce the influence of outliers. Similarly, all analyses will be repeated as stratified analyses (b - e below).

- b. Stratified according to < or > median age
- c. Stratified according to gender
- d. Stratified according to median years of education
- e. Stratified according to a clinical diagnosis of minor or major depression (for mobility and cognition)

3. Change in urinary severity index and depression category (based on the Geriatric Depression Scale) from baseline to 3 years. These analyses will be similar to the analyses for white matter hyperintensities in (1) and for mobility and cognition in (2), but using ordinal logistic regression.
 - a. According to treatment group (primary analysis)

$$\log(Y_{i1} > k / Y_{i1} \leq k) = \beta_{0k} + \beta_C x_i + \gamma_i$$

$$\log(Y_{i2} > k / Y_{i2} \leq k) = \beta_{0k} + \beta_C x_i + \beta_L + \beta_T x_i + \gamma_i$$

$$k = 1, \dots, m - 1$$

Here, x_i is the treatment group indicator for participant i as in (1) and (2); Y_{i1} is the ordinal urinary severity index score for participant i at time 1 (baseline), which takes values from 1 to m ; Y_{i2} is the ordinal urinary severity index score for participant i at time 2 (36 month follow-up); β_{0k} is interpreted as the log odds of having ordinal urinary severity index score k at baseline in the reference group; β_C is interpreted as the log odds ratio for a one unit higher urinary severity index score at baseline between the intervention group and

the reference group, and will be zero if the two groups are exactly comparable in their baseline values; β_L is interpreted as the log odds ratio for a one unit higher urinary severity index score between the 36 month follow up and baseline in the reference group; β_T is interpreted as an interaction, the difference in log odds ratios for a one unit higher urinary severity index score between between the 36 month follow up and baseline and between the intervention group and the reference group and thus the parameter of primary interest; and γ_i is a random intercept for participant i that addresses the correlation in mobility across the two time points.

This analysis makes the proportional odds assumption which will be checked by software.

- b. Stratified according to < or > median age
 - c. Stratified according to gender
 - d. Stratified according to median years of education
 - e. Stratified according to a clinical diagnosis of minor or major depression
4. Change in markers of tissue damage associated with microvascular disease of the brain (via diffusion tensor imaging (DTI)) from baseline to 3 years. Change in DTI will be evaluated as it relates to:
- a. Treatment group (primary analysis)

$$\begin{aligned} Y_{i1} &= \beta_0 + \beta_C x_i + \gamma_i + \varepsilon_{i1} \\ Y_{i2} &= \beta_0 + \beta_C x_i + \beta_L + \beta_T x_i + \gamma_i + \varepsilon_{i1} \end{aligned} \quad (1.1)$$

Here, x_i is the treatment group indicator for participant i (one for intervention, zero for comparison); Y_{i1} is the DTI for participant i at time 1 (baseline); Y_{i2} is the DTI for participant i at time 2 (36 month follow-up); β_0 is interpreted as the average DTI at baseline in the reference group; β_C is interpreted as the difference in the average DTI at baseline between the intervention group and the reference group and will be zero if the two groups are exactly comparable in their baseline values; β_L is interpreted as the average change in DTI between 36 month follow up and baseline in the reference group; β_T is interpreted as the difference average change in DTI between 36 month follow up and baseline between the intervention group and the reference group and thus the parameter of primary interest; γ_i is a random intercept for participant i that addresses the correlation in DTI across the two time points; and ε_{i1} and ε_{i2} are the residual error terms at baseline and follow-up, respectively. All analyses will be repeated as stratified analyses (b - e below).

- b. Stratified according to < or > median age
 - c. Stratified according to gender
 - d. Stratified according to median years of education
 - e. Stratified according to a clinical diagnosis of minor or major depression
 - f. Change from baseline in cognitive variables
 - g. Changes from baseline in mobility parameters
 - h. Changes from baseline in urinary function
5. Change in sleep scales (Pittsburgh Sleep Quality Index, and Epworth Sleep scale) and the SF-36 survey (QOL). Quality of sleep and quality of life will be evaluated as it relates to:
- a. Treatment assignment

$$Y_{i1} = \beta_0 + \beta_C x_i + \gamma_i + \varepsilon_{i1}$$

$$Y_{i2} = \beta_0 + \beta_C x_i + \beta_L + \beta_T x_i + \gamma_i + \varepsilon_{i2}$$

Here, x_i is the treatment group indicator for participant i (one for intervention, zero for comparison); Y_{i1} is the SF-36 score for participant i at time 1 (baseline); Y_{i2} is the SF-36 score for participant i at time 2 (36 month follow-up); β_0 is interpreted as the average SF-36 score at baseline in the reference group; β_C is interpreted as the difference in the average SF-36 score at baseline between the intervention group and the reference group and will be zero if the two groups are exactly comparable in their baseline values; β_L is interpreted as the average change in SF-36 between 36 month follow up and baseline in the reference group; β_T is interpreted as the difference average change in SF-36 between 36 month follow up and baseline between the intervention group and the reference group and thus the parameter of primary interest; γ_i is a random intercept for participant i that addresses the correlation in SF-36 across the two time points; and ε_{i1} and ε_{i2} are the residual error terms at baseline and follow-up, respectively. Above analysis will be repeated for Sleep Scales (Pittsburgh Sleep Quality Index, and Epworth Sleep scale), and then as stratified analyses (b - e below) for both Sleep and SF-36 scales.

- b. Stratified according to < or > median age
- c. Stratified according to gender
- d. Stratified according to years of education
- e. Stratified according to a clinical diagnosis of minor or major depression
- f. Change from baseline in cognitive variables
- g. Changes from baseline in mobility parameters
- h. Changes from baseline in urinary function
- i. Change from baseline in WMH (%)

6. Regression of changes from baseline in WMH as a mediator of changes from baseline in mobility, cognition, urinary function and depressive symptoms. These analyses will be based on the analyses in (2) and (3), but with the addition of mediation by and interaction with WMH using the methods of Vanderweele (REF below).

$$Y_{i1} = \beta_0 + \beta_C x_i + \gamma_i + \varepsilon_{i1}$$

$$Y_{i2} = \beta_0 + \beta_C x_i + \beta_L + \beta_T x_i + \gamma_i + \theta_M (m_{i2} - m_{i1}) + \theta_{INT} x_i (m_{i2} - m_{i1}) + \varepsilon_{i2}$$

$$m_{i2} - m_{i1} = \alpha_0 + \alpha_1 x_i + \delta_i$$

For mobility, cognition, and depression, variables are defined as in (1) with the following additions: δ_i is residual error in the model for change in WMH, and m_{i1} and m_{i2} are the values of WMH at baseline and follow-up, respectively. Some mediation measures of interest are as follows:

$$CDE = \beta_T$$

$$INT_{REF} = \theta_{INT} \alpha_0$$

$$INT_{MED} = \theta_{INT} \alpha_1$$

$$PIE = \theta_M \alpha_1$$

The controlled direct effect $CDE = \beta_T$ is the effect of treatment assignment in the absence of any WMH, $INT_{REF} = \theta_{INT} \alpha_0$ is the reference interaction between treatment assignment and WMH, $INT_{MED} = \theta_{INT} \alpha_1$ is the mediated interaction, and $PIE = \theta_M \alpha_1 x_i$ is the pure indirect effect. Combinations of these derived measures will be used to assess the degree of mediation, as described in VanderWeele. T.J. (2015). Explanation in Causal Inference: Methods for Mediation and Interaction, Oxford University Press. In particular, the proportion mediated is $\frac{INT_{REF} + INT_{MED} + PIE}{CDE + INT_{REF} + INT_{MED} + PIE}$.

Bootstrap standard errors and confidence intervals will be used for statistical inference, including estimation of standard errors and confidence intervals.

In secondary analyses, age, sex, and resultant ambulatory systolic BP at 36 months regardless of treatment assignment will be considered as mediators through similar methods. Specifically, age, sex, and systolic BP will replace $m_{i2} - m_{i1}$ in the model above and similar measures of interaction and mediation will be estimated.

7. Special Interest adverse events (falls, nervous system and vascular disorders) as related to numerous predictors of interest.

These outcomes are all count variables, so we use Poisson regression with each of the following predictors.

$$\log(\mu_i) = \log(n_i) + \beta_0 + \beta_1 x_i$$

Here μ_i is the count, n_i is the number of months in study, β_0 is the intercept with $\exp(\beta_0)$ interpreted as the rate of AE with mobility scale is zero, x_i is the predictor of interest, mobility scale and β_1 is the log rate ratio between groups and $\exp(\beta_1)$ is interpreted as the estimated ratio of rates for two subjects differing by one in their predictors of interest scale. This analysis will be repeated for the following predictors described below:

- a. Mobility variables
- b. Cognitive variables
- c. Treatment assignment
- d. Blood pressure
- e. Age
- f. Gender
- g. Number of classes of antihypertensive medications
- h. A clinical diagnosis of minor or major depression
- i. Sleep scales and SF-36 (QOL)

A final multivariate model will include all significant predictors.

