4.3 Study Enrollment Procedures at University of Connecticut Health Center

Study recruitment and enrollment. The study is a single-site randomized clinical trial that will be performed at the University of Connecticut Clinical Research Unit. Patients will be recruited from a variety of sources as described below. Three hundred patients will be enrolled into the trial in order to randomize 200 patients and complete 140 patients at 3 years of randomized treatment. Based on our prior experience in studying patients in this age group with hypertension and mild mobility issues, we project a 3-year attrition rate of approximately 30%. Recruitment will be carried out by several mechanisms, including: A) contacting former research participants from the Cardiology and Hypertension faculty practices, the Center on Aging, and Neurology who have agreed to be informed of future studies, B) publically posted advertisements in addition to advertisements on the internet, radio and newspapers, C) Recruitment presentations conducted at community health centers, faith-based organizations and senior centers in conjunction with BP community clinics.

Recruitment will be extended into the greater Hartford region to improve minority participation. Advertisements will state that we are seeking volunteers for a treatment study aimed at older patients with hypertension willing to join a study involving the evaluation and treatment of high blood pressure, mobility and cognitive function. The

ads will state that antihypertensive medication, clinical visits, brain imaging, and other testing will be provided at no cost.

Following voluntary assent, interested individuals will be screened by phone for inclusion/exclusion criteria. Those meeting initial screening criteria will be invited to a Consent/Evaluation Visit during which informed consent will be obtained, followed by a medical history, physical exam, and tests to determine eligibility. Those not meeting study criteria will be referred for medical care. Patients not able to read and understand the consent form will be excluded from the study.

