- b. We will repeat analyses 1a, 2a and 3a but with gait velocity at T₁₈, total WMH at T₁₈, and DTI indices at T₁₈ as the primary outcomes. A comparison of these analyses with analyses 1a and 1b will determine the time course of the intervention's effects. In particular, it will be important to determine if these effects occur early (T₁₈) or require a 3-year treatment period. In addition, for participants who are present at T₁₈ but not T₃₆, the data from T₁₈ will be used to estimate the effect of informative loss to follow-up. (See Missing Data)
- c. We will further examine the progression of mobility and WMH changes using a progression model using methods adapted from Diggle:³⁶

$$Y_{i0} = b_{i0} + \beta_T (X_i) + \text{cross sectional covariates} + \text{residual error}$$

$$Y_{i18} = b_{i0} + \beta_T (X_i) + \beta_L + \beta_E (X_i) + \text{cross sectional covariates} + \text{longitudinal covariates} + \text{residual error}$$

$$Y_{i36} = b_{i0} + \beta_T (X_i) + \beta_L^* + \beta_E^* (X_i) + \text{cross sectional covariates} + \text{longitudinal covariates} + \text{residual error}$$

Here, Y_{i0} , Y_{i18} , and Y_{i36} are the outcomes (mobility or imaging) at T_0 , T_{18} , and T_{36} for study participant i , and X_i is the treatment group assignment indicator for study participant i , and b_{i0} is a random intercept used to account for the fact that repeated measurements on individuals are not independent; the other β_j 's are fixed effects in this example although we will consider the possibility that treating them as random effects will add to the model fit. The model will be fit as a linear mixed model.^{37, 38} The parameters of interest are β_E , and β_E^* , the difference in the outcome progression rate (mobility or imaging) between the treatment groups at T_{18} and T_{36} . If the difference in the rate of progression is constant during follow-up, we would expect β_E^* to approximately equal $2 \times \beta_E$. This allows a more powerful and rigorous test of whether the intervention's effects are manifested quickly or over the long-term. Additional secondary analyses will use the T_{18} data to determine temporal continuity of the trends and as a partial assessment of the effect of dropout. Additional secondary analyses will use logistic regression with severity of urinary incontinence at T_{36} and T_{18} as an ordinal outcome.

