8.3 Sample Size and Randomization

We conservatively estimate that at least 140 of the original 200 participants will complete assessments at 35 months. We analyzed a subset of participants in our earlier observational study in order to mimic the results of the two treatment groups we expect to see in the intervention study. For a standard care arm, we selected participants in the observational study who had 24 hour systolic BP between 140 and 150 mmHg, inclusive, at follow-up, and for the intensive treatment arm, we selected participants with 24 hour Systolic BP between 120 and 130 mmHg, inclusive, at follow-up. A regression of gait velocity over 8 feet on our covariates age, sex, and 24 hour systolic BP at baseline showed an r^2 of 0.1267. If we see similar results in the intervention study, 140 participants (70 in each group) will give us 85% power to observe an increase in r^2 of 0.0533 to 0.1800. In our prior observational study, we saw an increase in r^2 of 0.1082 to 0.2349, with a difference in gait speed between the two simulated treatment groups of 0.15m./sec. While the 0.15m/sec gait speed difference between the low and high BP groups appears small, it represents only 2 years of observation. Mobility impairment linked to WMH is a long-term decremental process that limits gait velocity over 10 or more years. Thus a “small” 2-year differential is both believable and meaningful. We are therefore confident that the proposed study has ample power to find smaller yet clinically significant effects for our primary outcome. A regression of total WMH on covariates age, sex, and 24 hour systolic BP at baseline showed an r^2 of 0.1162. Similar results in the intervention study imply 85% power to observe an increase in r^2 of 0.0540 for the effect of the treatment arm, to 0.1702. We actually observed an increase of 0.0861, to 0.2023, in the prior observational study, corresponding to a difference between the two simulated treatment groups of 0.93% total WMH.

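### The SAP's treatment-effect models use only baseline and month 36 and are not reconciled with the month-18 and three-visit analyses in protocol section 8.2

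*SAP*

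**What the plan says.** **Protocol.** Section 3 and the schedule in section 5.5 place MRI, mobility, cognitive and urinary assessments at baseline, month 18 and month 36. The 2012 addendum does the same for the sleep scales. In section 8.2 (Hypotheses and Statistical Analyses), analysis b repeats the regressions at month 18, saying "it will be important to determine if these effects occur early" or need three years, and uses month-18 data to study informative loss among patients absent at month 36. Analysis c is a linear mixed model over all three visits with one treatment effect at month 18 and another at month 36. The section extends month-18 or three-visit models to cognition, incontinence, Hypothesis 4 and mediation.

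**SAP (24 September 2018, before the October 2018 lock).** Each treatment-effect model is a pair of equations. In item 1a the second response "is the WMH % for participant i at time 2 (36 month follow-up"); in item 2a it "is the mobility score for participant i at time 2 (36 month follow-up"). Items 3a, 4a and 5a have the same form, and items 1a to 4a label the treatment comparison as primary. Item 6, "Regression of changes from baseline in WMH as a mediator of changes from baseline in mobility, cognition, urinary function and depressive symptoms", builds on these models. The SAP contains no month-18 term and no missing-data method. Its introduction says that secondary analyses have been added; it withdraws nothing.

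**Attrition.** Protocol 4.3 states: "we project a 3-year attrition rate of approximately 30"%.

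**The concern.** For the same outcomes, one document has a three-visit mixed model and the later one has a two-visit model labelled primary, and neither says which governs. An analyst working from the SAP at lock could report every treatment effect without opening the month-18 data. Three things would follow.

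- The timing question that the protocol calls important would go unanswered, because a two-visit model has no month-18 effect to estimate.
- Patients assessed at month 18 and not afterwards would enter with a baseline value alone.
- The 36-month contrast would rest on a stronger missing-data assumption. With two visits, dropout may depend only on arm and baseline. With three, it may also depend on the month-18 value, which is likely to be the most informative observation on a patient who leaves later.

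**Working it through.** **1. The plan's own figure.** Protocol 8.3 says that "140 participants (70 in each group) will give us 85% power to observe an increase in" r² of 0.0533, to 0.1800. The baseline model is "A regression of gait velocity over 8 feet on our covariates age, sex, and 24 hour systolic BP at baseline", with r² 0.1267. Alpha is not stated; two-sided 0.05 is assumed.
- f² = 0.0533 / (1 − 0.1800) = 0.0650
- noncentrality = 140 × 0.0650 = 9.10, on 1 and 135 degrees of freedom
- power = 84.97%, matching the stated 85%
- 140 / (1 − 0.30) = 200, matching the randomised number

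Neither figure uses month 18, so the sample size is not in question.

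**2. Patients affected.** At 30% attrition, 70 per arm reach month 36. The number seen at month 18 is not given. Assuming 75 to 90 per arm, 2 × (75 − 70) = 10 to 2 × (90 − 70) = 40 patients have a month-18 value and no month-36 value, before any recovery through exit tests.

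**3. Precision.** Take 100 per arm at baseline, n18 at month 18 and 70 at month 36, unit variance and data missing at random. The per-arm variance of the estimated change to month 36 is:
- two visits: V(36|0)/70 + (β − 1)²/100, where β is the slope of month 36 on baseline
- three visits: V(36|0,18)/70 + b18² × V(18|0)/n18 + (β − 1)²/100, where b18 is the partial slope on month 18

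Worked case, all correlations 0.7 and n18 = 85:
- two visits: 0.51/70 + 0.09/100 = 0.00819
- three visits: b18 = 0.7/1.7 = 0.412 and V(36|0,18) = 0.4235, so 0.4235/70 + 0.1696 × 0.51/85 + 0.09/100 = 0.00797
- ratio 0.973; a test with 85% power moves to 85.9%

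Over correlations 0.5 to 0.9 (equal, or decaying with time) and n18 of 75 to 90, variance falls by 0.6 to 9.3% and 85% power becomes 85.2 to 88.2%. Simulation over similar settings put the fall at about 1 to 11%.

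**4. Bias in gait speed.** The cohort data came "with a difference in gait speed between the two simulated treatment groups of 0.15m./sec", with an r² gain of 0.1082. Taking equal groups, and arm uncorrelated with the covariates:
- SD = √(0.25 × 0.15² / 0.1082) = 0.228 m/s

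This is an upper bound, because correlation between arm and covariates lowers it. Trials were simulated with no true effect, 100 per arm, about 31% missing at month 36 and visit correlations of 0.5 to 0.8. Dropout after month 18 was tied more strongly to slow month-18 gait in the intensive arm.
- two-visit bias: about 0.005 to 0.015 m/s in favour of intensive treatment
- three-visit bias: about 0.003 m/s or less

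For scale, the difference detectable at 85% power is 0.15 × √(0.0533/0.1082) = 0.105 m/s, so the bias is 0.005/0.105 = 5% to 0.015/0.105 = 14% of it. With 70 per arm the standard error is 0.228 × √(4(1 − ρ)/70), which is 0.039 at ρ = 0.5 and 0.024 at ρ = 0.8. The bias is then typically half a standard error or less. Setting the largest bias against the smallest standard error, which need not come from the same setting, gives 0.015/0.024 = 0.6. Stronger assumed selection gives larger values. Without arm-dependent selection there is no such bias.

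**The case against.** A reader might infer three stronger things, and the documents support none of them.

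**That month 18 is unused for every outcome.** This is true of the SAP read alone. Protocol 8.2 still specifies month-18 and three-visit analyses, and the SAP presents itself as adding to the plan. Its primary label can be read as the main comparison within each item, ahead of the strata. The protocol's primary efficacy analysis, gait velocity at month 36, never used month 18. What remains is that nobody has written down how the two sets of models relate.

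**That every late dropout contributes only a baseline value.** Section 5.6.4 gives the final-visit tests to patients who leave after at least 18 months. Section 6 invites those who stop treatment to the month-18 and month-36 assessments. Section 8.2 adds telephone mobility assessment with multiple imputation or joint modelling. These would recover some patients. They will not reach everyone, the telephone route covers mobility only, and the SAP does not say whether an exit test counts as time 2.

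**That a planned time-ordering of WMH accrual before functional decline was dropped.** Item 6 does measure mediator and outcome change over the same interval. But the protocol never gave month 18 an ordering role: Hypotheses 4 to 6 relate imaging and function at the same visit, with baseline imaging as a further predictor, and Hypothesis 5 results are called preliminary.

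It is also fair to say that the bias depends on a dropout pattern for which the documents give no evidence, and that the simulation ignores exit tests.

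**Conclusion.** The point holds as a failure to reconcile. SAP items 1a to 5a neither carry over the protocol's month-18 and three-visit analyses nor state their standing, and they do not place early-exit tests in time. The most certain loss, if the SAP is followed alone, is the month-18 effect estimate; this needs no assumption. The effect on the 36-month contrast is modest: about 1 to 11% of variance under assumed correlations and missing at random, and a gait bias of roughly 0.005 to 0.015 m/s only under arm-dependent dropout related to month-18 gait. The stated 85% power and 200 patients are unaffected. The change is worth making before lock because the data are already planned and the cost is low, not because the 36-month result is shown to be wrong.

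**What to change.** - In SAP items 1a to 5a, fit visits 0, 18 and 36 with separate arm-by-visit terms: unstructured covariance for continuous outcomes, an ordinal mixed model for item 3. Include every randomised patient with any visit.
- Keep the month-36 contrast as the main result and report the month-18 contrast beside it.
- State that protocol 8.2b and 8.2c remain in force, and which model governs where both documents cover an outcome.
- State how exit tests are placed in time, by visit windows or actual month, so that a test soon after month 18 is not analysed as a month-36 value.
- Optionally, add to item 6 a supportive model with WMH change from 0 to 18 months as mediator of function at month 36, adjusted for baseline. It misses accrual after month 18, so it would sit beside the 0-to-36 model and not replace it.

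The cost is SAP wording and a little extra programming before lock. No new data are needed.
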